5.2.7 Other Modalities and Procedures

5.2.7.1 Surgery: Surgery will be performed one to four weeks after completion of capecitabine therapy. If surgery is delayed beyond four weeks after completion of capecitabine, the patient will be taken off study. At laparotomy, the liver and pancreas will be examined by palpation and inspection. In the absence of metastases, tumor mobilization and surgical resection will be performed. A pancreaticoduodenectomy (Whipple procedure) or distal pancreatectomy with standard lymphadenectomy will be done. This involves dissection up to the superior mesenteric artery, with skeletonization of the right lateral and anterior aspects of the vessels. Feeding jejunostomy and gastrostomy tubes may be placed at the discretion of the operating surgeon.

5.2.7.2 Pathology: Processing the specimen and pathology will be reported according to the AJCC Cancer Staging Manual, 6th Edition. Pancreatic transection margin, and the bile duct margin will be evaluated on frozen section. Recorded on permanent section will be: tumor size, degree of differentiation (well, moderate, poor), lymph node status, and margin status.

5.2.7.3 Chemotherapy: Patients may receive adjuvant chemotherapy after at the discretion of the treating investigator. If adjuvant chemotherapy is administered, at minimum, administration of FOLFIRINOX therapy will be contingent on patients meeting original inclusion criteria (lab parameters and performance status). Physicians may opt to provide FOLFOX or FOLFIRI in the postoperative setting, with the full FOLFIRINOX regimen administered only when the patient is able to tolerate this therapy. If there is evidence of progression, patients will be withdrawn

from the study and as per NCCN guidelines, proceed to second-line therapy (likely gemcitabine-based chemotherapy.) Appropriate dose reductions and modifications can be made at the discretion of the treating physician.

5.3 General Concomitant Medication and Supportive Care Guidelines:

5.4 Duration of Therapy

Duration of therapy will depend on individual response, evidence of disease progression and tolerance. In the absence of treatment delays due to adverse events, treatment may continue until one of the following criteria applies:

- Disease progression,
- Intercurrent illness that prevents further administration of treatment,
- Unacceptable adverse event(s),
- Participant decides to withdraw from the study, or
- General or specific changes in the participant's condition render the participant unacceptable for further treatment in the opinion of the treating investigator.

5.5 Duration of Follow Up

Study participants will be in active follow up after completion of neoadjuvant treatment and surgery per study guidelines, as outlined above, except in the case of documented progression, at which time they will be followed for survival only. Participants removed from study for

unacceptable adverse events will be followed until resolution or stabilization of the adverse event.

5.6 Criteria for Removal from Study

Participants will be removed from study when any of the criteria listed in Section 5.4 applies. The reason for study removal and the date the participant was removed must be documented in the study-specific case report form (CRF). Alternative care options will be discussed with the participant.

In the event of unusual or life-threatening complications, participating investigators must immediately notify the Principal Investigator [name]. at [REDACTED]

6 EXPECTED TOXICITIES AND DOSING DELAYS/MODIFICATIONS

Dose delays and modifications will be made using the following recommendations. Toxicity assessments will be done using the CTEP Active Version of the NCI Common Terminology Criteria for Adverse Events (CTCAE) which is identified and located on the CTEP website at: http://ctep.cancer.gov/protocolDevelopment/electronic_applications/ctc.htm.

If possible, symptoms should be managed symptomatically. In the case of toxicity, appropriate medical treatment should be used (including anti-emetics, anti-diarrheals, etc.).

All adverse events experienced by participants will be collected from the time of the first dose of study treatment, through the study and until the final study visit. Participants continuing to experience toxicity at the off study visit may be contacted for additional assessments until the toxicity has resolved or is deemed irreversible.

6.1 Anticipated Toxicities

A list of the adverse events and potential risks associated with the agents administered in this study appear below and will determine whether dose delays and modifications will be made or whether the event requires expedited reporting **in addition** to routine reporting.

6.1.1 FOLFIRINOX Therapy

6.1.1.1 Anticipated Hematologic adverse events

Below is the table of adverse events associated with the FOLFIRINOX regimen in the Prodiges-4/ACCORD trial in patients with advanced pancreatic adenocarcinoma.

AE, % per patient	Folfirinox	
	N=171 (from NEJM 2011)	
	All	Grade 3/4
Neutropenia	79.9	45.7
Febrile Neutropenia	5.4	
Anemia	90.4	7.8
Thrombocytopenia	75.2	9.1

6.1.1.2 Anticipated Non-Hematologic adverse events

Below is the table of adverse events associated with the FOLFIRINOX regimen in the Prodiges-4/ACCORD trial in patients with advanced pancreatic adenocarcinoma.

AE, % per patient	Folfirinox N=168 (from ASCO 2010)	
	All	Grade 3/4
Infection without neutropenia	6	1.2
Peripheral neuropathy	70.5	9
Vomiting	61.4	14.5

Fatigue	87.3	23.2
Diarrhea	73.3	12.7
Alopecia (grade 2)	32.5	(11.4)
ALT	64.8	7.3

6.1.2 Radiation Therapy

The most common toxicities of radiation therapy are fatigue, nausea, abdominal pain, diarrhea, indigestion, vomiting, weight loss and anorexia. Other toxicities may include radiation fibrosis if surgery is delayed too long. Much less common toxicities could include liver damage, kidney damage, delayed wound healing, and late second malignancies.

6.1.3 Capecitabine

The most common toxicities of capecitabine are diarrhea, indigestion, nausea, vomiting, weight loss, anorexia, and hand-foot syndrome (skin changes and tenderness of hands and feet, especially fingers and toes). Other toxicities may include neutropenia, thrombocytopenia, anemia, cutaneous eruptions, alopecia, fever, and fatigue or general malaise. Much less common toxicities could include allergic reactions and coronary vasospasm.

6.2 Toxicity Management

6.2.1 FOLFIRINOX therapy

“One cycle” will constitute one administration of FOLFIRINOX therapy, administered on Day 1-3. Each cycle will be 14 days long, and will be repeated every 14 days, unless further dose delay is warranted by toxicities. Cycle adjustments of +3/-1 days may be made at the discretion of the treating physician. A break in therapy of up to one week for restaging is allowed.

The table below indicates potential dose levels for each of the agents for which dose modifications will be allowed. Dose adjustments of each agent may be made independently based on the specific types of toxicities observed. Only those agents specified in the sections below should be dose-reduced.

Patients who require multiple dose reductions during a cycle for grade 2 toxicity may, at the physician's discretion, begin the following cycle at one dose level higher than the current dose reduction. If dose reduction beyond -3 for any agent is required, that agent should be discontinued.

Agent*	Oxaliplatin	Irinotecan	5-FU Bolus	5-FU Infusion
Initial Dose	85 mg/m ²	180 mg/m ²	400 mg/m ²	2400 mg/m ² per 46-48 hours
Level -1	65 mg/m ²	150 mg/m ²	320 mg/m ²	1920 mg/m ² per 46-48 hrs
Level -2	50 mg/m ²	120 mg/m ²	270 mg/m ²	1600 mg/m ² per 46-48 hrs
Level -3	40 mg/m ²	100 mg/m ²	230 mg/m ²	1360 mg/m ² per 46-48 hrs

Leucovorin dose is always 400 mg/m², IV given prior to the infusion of 5-FU. If any infusion of 5-FU is to be skipped, leucovorin must also be skipped. Initial doses may be reduced, if necessary, at the physician's discretion.

If a patient has undergone biliary stent placement prior to enrollment, the following treatment guidelines will apply for Cycles 1 and 2. If ALT and AST are elevated beyond 2.5 x the upper limit of normal at time of study enrollment, but demonstrate two consecutive down-trending values, the patient should begin treatment without Irinotecan, or with dose-reduced Irinotecan if clinically indicated. The agents 5-FU and Oxaliplatin may be given during Cycle 1 with Irinotecan incorporated as laboratory values permit. If total bilirubin is elevated above 2.0 mg/dl at time of enrollment, the patient may begin Cycle 1 with full dose 5-FU and Oxaliplatin, with Irinotecan incorporated as laboratory values permit. If total bilirubin is elevated between the upper limit of normal and 2.0 mg/dl at time of enrollment, the patient

may receive full dose 5-FU and Oxaliplatin, with dose-reduced Irinotecan. Irinotecan may be increased to full dose in the first or second cycle if laboratory values permit.

6.2.1.1 Hematologic toxicities

The following dose modifications are based on toxicity demonstrated during a mid-cycle visit and/or at the time of laboratory assessment for planned administration of the next cycle of therapy (for example on the planned day of administration of Cycle 2 Day 1 after completing the 14-day period constituting Cycle 1.) As the Grade 2-4 neutropenia rate in the PRODIGE-ACCORD trial was 79.9%, in this trial prophylactic GM-CSF (Neulasta) will be administered 24-48 hours after discontinuation of continuous infusion 5-FU.

Dose Reduction Table for Hematologic Toxicity

(Note: DR = Dose Reduction)

Hematologic Toxicity on the Day of Treatment (D1)	Action	Oxaliplatin	Irinotecan	5-FU Bolus (Leucovorin follows protocol for 5FU bolus)	5-FU Continuous Infusion
Neutropenia G2 (ANC 1500-1000) – all patients should have Neulasta support per institutional guidelines	HOLD ALL THERAPY	Hold until ANC \geq 1500, resume without dose reduction	Hold until ANC \geq 1500, resume without dose reduction	Hold until ANC \geq 1500, resume without dose reduction	Hold until ANC \geq 1500, resume without dose reduction
Neutropenia G3-4, Febrile neutropenia (ANC 1000-500, <500)	HOLD ALL THERAPY, Supportive care and antibiotics per institutional guidelines	Hold until ANC \geq 1500, resume @ permanent DL-1 level once resolved	Hold until ANC \geq 1500, resume @ permanent DL-1 level once resolved	Hold until ANC \geq 1500, resume @ permanent DL-1 level once resolved	Hold until ANC \geq 1500, resume @ permanent DL-1 level once resolved
Thrombocytopenia G1 (LLN – 75K)	Treat with DR Oxaliplatin	Treat at permanent DL -1	No reduction	No reduction	No reduction

Thrombocytopenia G2 (75K – 50K)	HOLD ALL THERAPY	Hold until resolved to >100K, resume at permanent DL-1	Hold until resolved to >100K, no reduction	Hold until resolved to >100K, No reduction	Hold until resolved to >100K, No reduction
Thrombocytopenia G3-4 (50K – 25K, <25K)	HOLD ALL THERAPY	Hold until resolved to >100K. Resume @ permanent DL-1 if resolved in 1 wk, permanent DL -2 if >1 wk to resolve	Hold until resolved to >100K. Resume @ permanent DL-1.	Hold until resolved to >100K	Hold until resolved to >100K

6.2.1.2 Gastrointestinal toxicities:

Lacrimation, rhinorrhea, miosis, diaphoresis, hot flashes, flushing, abdominal cramping, diarrhea, or other symptoms of early cholinergic syndrome may occur during or shortly after receiving irinotecan. Atropine, 0.25-1.0 mg IV or SC may be used to treat these symptoms. In patients with troublesome or recurrent symptoms, prophylactic administration of atropine shortly before irinotecan therapy may be considered. Additional antidiarrheal measures may be used at the discretion of the treating physician. Anticholinergics should be used with caution in patients with potential contraindications (e.g., obstructive uropathy, glaucoma, tachycardia, etc.)

Late diarrhea (e.g., developing more than 24 hours after irinotecan) should be managed with loperamide. The following dose modifications are based on toxicity experienced during a cycle (i.e., after Day 1 of any cycle):

The following dose modifications are based the grade of mucositis seen on the day of treatment for any day after Day 1 in any cycle.

Dose Reduction Table for Non-Hematologic Toxicity (Except Neuropathy)

(Note: DR = Dose Reduction)

Non-hematologic Toxicity on the Day of Treatment (D1)	Action	Oxaliplatin	Irinotecan	5-FU Bolus (Leucovorin DR follows protocol for 5FU bolus DR)	5-FU Continuous Infusion
Diarrhea G2	DR Irinotecan Bolus 5FU, and CI 5FU	No reduction	Treat at permanent DL -1	Treat at permanent DL -1	Treat at permanent DL -1
Diarrhea G 3-4	DR Irinotecan and CI 5FU and eliminate Bolus 5FU	No reduction	Treat at permanent DL -1	Permanently eliminate bolus	Treat at permanent DL -1
Mucositis G2	DR Bolus and CI 5FU	No reduction	No reduction	Treat at permanent DL -1	Treat at permanent DL -1
Mucositis G3-4	DR Irinotecan and CI 5FU, eliminate Bolus 5FU	No reduction	Treat at permanent DL -1	Permanently eliminate bolus	Treat at permanent DL -1
Nausea/Vomiting G3-4	HOLD ALL THERAPY	Maximal antiemetic therapy. Hold until resolved to G2 or less, resume @ permanent DL-1	Maximal antiemetic therapy. Hold until resolved to G2 or less, resume @ permanent DL-1	Maximal antiemetic therapy. Hold until resolved to G2 or less, resume @ permanent DL-1	Maximal antiemetic therapy. Hold until resolved to G2 or less, resume @ permanent DL-1

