3 ELIGIBILITY CRITERIA

3.1 Inclusion Criteria:

Participants must meet the following criteria on screening examination to be eligible to participate in the study:

- 3.1.1** Cytologic or histologic proof pancreatic ductal carcinoma is required prior to study entry. Diagnosis must be confirmed by the MGH pathology department.
- 3.1.2** No evidence of metastatic disease as determined by chest CT scan, abdomen/pelvis CT scan (or MRI with gadolinium and/or manganese) within six weeks of study entry. All patients must be staged with a physical exam, chest CT, abdominal CT with intravenous contrast (or Abd MRI with gadolinium and/or manganese).
- 3.1.3** Staging laparoscopy is not required at the outset of the trial, including in patients who might otherwise receive staging laparoscopy per NCCN guidelines (high-risk body and tail lesions), because patients will receive systemic chemotherapy at equivalent dose to patients who have documented Stage IV disease.
- 3.1.4** Patients who are deemed ‘borderline resectable’ will be included. Borderline resectable is defined by the NCCN as tumors with venous involvement of the SMV/portal vein demonstrating tumor abutment with or without impingement and narrowing of the lumen, either tumor thrombus or encasement but with suitable vessel proximal and distal to the area of vessel involvement, allowing for safe resection or reconstruction; gastroduodenal artery encasement up to the hepatic artery with either short segment encasement or direct abutment of the hepatic artery, without extension to the celiac axis; or tumor abutment of the SMA not to exceed greater than 180 degrees of the circumference of the vessel wall. Tumors involving retroperitoneal structures that can be surgically removed (ie. kidney), will also be included.
- 3.1.5** Patients must be 18 years old or older. There will be no upper age restriction.
- 3.1.6** Patients with ECOG-Performance Status of 0 or 1 are eligible.

3.1.7 Life expectancy of greater than 3 months.

3.1.8 Lab Values within one week of study entry:

ANC \geq 1000 cells/mm³

Platelet count at least 100,000 cells/mm³.

AST and ALT \leq 2.5 x upper limit of normal, OR two consecutive downtrending values for patients who have undergone biliary stenting.

Total Bilirubin \leq 1.5 x upper limit of normal,

OR, for patients who have undergone biliary stenting, Total bilirubin \leq 2.0 OR two downtrending values

Serum Creatinine \leq 1.5 mg/dl

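### From Cycle 2, an unchanged platelet count or ANC that met the entry criteria is classed as toxicity by the hematologic dose table, which makes no exception for baseline values

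*Combined protocol and SAP*

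**What the plan says.** **Entry.** Section 3.1.8 requires, within a week of study entry, "ANC \geq 1000 cells/mm³" and "Platelet count at least 100,000 cells/mm³".

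**Treatment.** The hematologic dose reduction table in 6.2.1.1 works on absolute counts.

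- The row "Neutropenia G2 (ANC 1500-1000") holds all therapy until the ANC is at least 1,500. Each drug column then says "resume without dose reduction".
- The row "Thrombocytopenia G1 (LLN – 75K") keeps the other drugs at full dose, but the oxaliplatin entry is "Treat at permanent DL -1".
- The G2 and G3-4 platelet rows hold all therapy until the count has resolved to above 100K.

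**When the table applies.** Its lead-in refers to toxicity seen at a mid-cycle visit or at the laboratory check before the next cycle, and gives Cycle 2 Day 1 as the example. The first column heading refers to Day 1 of treatment without naming a cycle.

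**Dose levels.** Section 6.2.1 sets oxaliplatin at 85 mg/m² initially and 65 mg/m² at level -1. Section 5.2 allows up to 8 cycles.

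**The concern.** The entry floors lie inside the bands that the table calls toxicity, and the table does not ask whether the count has fallen since enrollment. A patient can therefore qualify with a given platelet count, keep it, and have oxaliplatin permanently reduced because of it. Delivered dose would then fall for a pre-existing value, and the toxicity record would attribute that value to treatment.

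The protocol does link entry values to dosing elsewhere. Sections 5.1 and 6.2.1 give explicit early-cycle rules for stented patients who enter with raised transaminases or bilirubin. Blood counts have no such rule. In a 50-patient single-arm trial, a gap of this kind means that similar patients may be handled differently from one treating physician to the next.

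**Working it through.** The plan gives no figure of its own on this point, so the check compares ranges and then works out the dose consequence.

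**1. Overlap of ranges**

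| Count | Eligible (3.1.8) | Table band (6.2.1.1) | Overlap | Action in table |
|---|---|---|---|---|
| ANC | at least 1,000 | 1,000 to below 1,500 | 1,000-1,499 | hold all; no reduction on resuming |
| Platelets | at least 100K | 75K up to the LLN | 100K up to the LLN | oxaliplatin permanently at level -1 |

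The ANC overlap is 1,500 - 1,000 = 500 cells/mm³ wide. An ANC of exactly 1,000 is named both in the G2 row and in the row below it; it is taken here as G2.

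The platelet overlap depends on the LLN, for which the documents give no number. Its width is LLN - 100K:

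- LLN 130K (assumed): 30K
- LLN 140K (assumed): 40K
- LLN 150K (assumed): 50K
- LLN of 100K or less: no overlap

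A patient with an ANC of at least 1,500 and platelets at or above the LLN is unaffected.

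**2. Size of the oxaliplatin reduction**

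- Per affected cycle: 65/85 - 1 = -23.5%.
- Eight cycles, row first met at Cycle 2: 85 + 7 × 65 = 540 mg/m², against 8 × 85 = 680 mg/m². The change is 540/680 - 1 = -20.6%.
- Four cycles, as an illustration of a shorter course: 85 + 3 × 65 = 280 mg/m², against 4 × 85 = 340 mg/m². The change is 280/340 - 1 = -17.6%.

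**3. The platelet rows against each other**

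Take a count of 110K and assume an LLN above that. By 3.1.8 it is an acceptable entry value. By the G2 and G3-4 rows it is a resolved value at which treatment may resume. By the G1 row it is toxicity that calls for a permanent reduction. For a patient already at level -1 after a G2 event, the G1 row as worded changes nothing, so the inconsistency there is one of classification. For a patient with no earlier event, it decides the dose.

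**4. Whether another rule removes the problem**

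Section 6.2.1 lets a patient who needed multiple reductions for grade 2 toxicity go back up one level. That clause does not clearly reach a G1 row whose reduction is labeled permanent.

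**The case against.** Several counter-arguments carry weight.

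- **Timing.** A reader might infer from the Day 1 column heading that an eligible patient with an ANC of 1,200 cannot start Cycle 1, and so drops out of the R0 denominator in 14.2. The documents do not support this. The lead-in points to the next cycle. The non-hematologic table has the same style of heading over rules for toxicity arising after treatment has begun. Even if the row applied on Cycle 1 Day 1, it prescribes a delay, and patients who start stay in the denominator. What stands is that the heading leaves Cycle 1 Day 1 unclear.
- **Both limits can be obeyed.** Eligibility is checked once and the table applies later, so enrolling a patient and then holding or reducing treatment breaks no rule. This is correct. The problem is what the rules produce when followed, not that they cannot be followed.
- **Growth factor.** Section 6.2.1.1 provides prophylactic Neulasta after each 5-FU infusion, which may make a persistent ANC of 1,000-1,499 uncommon. This largely answers the ANC row, although the text on prophylaxis in 5.3 is garbled. The documents claim no such effect on platelets.
- **Meaning of toxicity.** Section 11.1.1 defines an adverse event as something that arises or worsens after the first dose or a protocol procedure, so an unchanged count is arguably not toxicity. But that is a reporting definition, and the table does not cite it. It also excludes most laboratory values that need no action, so it fits poorly as the trigger for a table built on counts.
- **Discretion.** Section 6 calls these rules recommendations, and 5.2.2 leaves oxaliplatin adjustments to the oncologist. This softens the effect without saying how a baseline value should be treated.
- **Adjuvant phase.** A reader might see the same conflict in 5.2.7.3, where "administration of FOLFIRINOX therapy will be contingent on patients meeting original inclusion criteria (lab parameters and performance status"). That section presents the entry criteria as a minimum, so stricter treatment-day rules can sit on top of them, and adjuvant therapy is optional. No real conflict arises there.

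**Conclusion.** The point holds for Cycle 2 onward, and mainly for platelets. As written, an eligible patient whose platelets simply remain between 100K and the LLN meets a row requiring a permanent oxaliplatin reduction: -23.5% per affected cycle, and at most about -21% cumulatively if all 8 cycles are given and the row is first met at Cycle 2. For the ANC the consequence is a delay only, and possibly an uncommon one.

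The conclusion assumes an LLN above 100K, a count that stays in the band, and a physician who follows the table without using discretion. The documents do not allow an estimate of how many patients are affected. No effect on the R0 denominator or on the 16-of-50 decision rule is shown. The point is worth correcting because a stated rule, followed literally, treats a qualifying baseline value as harm from treatment, and because the platelet rows disagree among themselves.

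**What to change.** Amend the protocol to:

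1. reconcile 3.1.8 with the ANC 1,000-1,500 row and the platelet LLN-75K row of 6.2.1.1;
2. reconcile the G1 platelet row with the recovery threshold used in the G2 and G3-4 rows;
3. state whether the table applies on Cycle 1 Day 1;
4. state how a count that met the entry criteria, and has not changed, is handled in later cycles.

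Which limit applies is for the sponsor's clinicians to decide; no threshold or dose is proposed here. The cost is one amendment. No extra tests are needed, because the calendar in Section 9 already has a blood count before study and on Day 1 of each FOLFIRINOX cycle.

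### The FOLFIRINOX dose table sets a reduced dose for grade 3-4 diarrhea and mucositis but, unlike the other grade 3-4 rows, no hold and no recovery level before re-dosing

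*Combined protocol and SAP*

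**What the plan says.** Sections 6.2.1.1 and 6.2.1.2 each contain a dose table for FOLFIRINOX. In the non-hematologic table, the action for grade 3-4 diarrhea is "DR Irinotecan and CI 5FU and eliminate Bolus 5FU" and for grade 3-4 mucositis "DR Irinotecan and CI 5FU, eliminate Bolus 5FU". The drug columns of both rows put irinotecan and infusional 5-FU at permanent dose level -1, drop the 5-FU bolus for good, and leave oxaliplatin unreduced.

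In the same table, the grade 3-4 nausea/vomiting row stops all drugs and adds "Hold until resolved to G2 or less, resume @ permanent DL-1".

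The text on when the table applies is mixed. The column header reads "Non-hematologic Toxicity on the Day of Treatment (D1". The lead-in for diarrhea makes the changes "based on toxicity experienced during a cycle (i.e., after Day 1 of any cycle", and the one for mucositis uses the "grade of mucositis seen on the day of treatment for any day after Day 1 in any cycle".

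Two general provisions bear on the point. Section 6.2.1 allows the 14-day cycle to be delayed for toxicity, and section 6 describes its dosing rules as recommendations.

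**The concern.** Sections 2.1.1 and 2.1.3 name the same two dose-limiting toxicities, neutropenia and diarrhea, for 5-FU and for irinotecan. The tables treat them differently. Neutropenia stops all drugs from grade 2 upward, even though at grade 2 the patient may then "resume without dose reduction". Diarrhea has no written hold at any grade, including grade 4, and both responsible drugs continue at a lower dose.

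At stake is the safety of an individual patient who reaches the planned Day 1 with grade 3-4 diarrhea or mucositis. Section 2.1.1 warns that diarrhea on 5-FU often leads to dehydration. Section 6.2.1.2 offers loperamide for late diarrhea, but section 2.1.3 notes that such agents usually fail once diarrhea is grade 4.

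**Working it through.** **1. The grade 3-4 rows side by side (sections 6.2.1.1 and 6.2.1.2)**

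| Row | Holds all drugs? | Recovery level |
|---|---|---|
| Neutropenia / febrile neutropenia | Yes | ANC at least 1500 |
| Thrombocytopenia | Yes | Platelets above 100K |
| Nausea/vomiting | Yes | Grade 2 or less |
| Diarrhea | No | None |
| Mucositis | No | None |

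Of five rows, three have a hold with a recovery level and two have neither.

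**2. Which reading of the two rows is right?**

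- *Reading A, from the header.* The toxicity is present on Day 1 and the patient is dosed that day at the reduced level. The wording supports this. The grade 1 thrombocytopenia row uses the same treat-at-level--1 instruction for oxaliplatin, and there the patient is clearly dosed despite the toxicity.
- *Reading B, from the lead-ins.* The toxicity occurred during the cycle and the row only sets the dose level for the next one. This is plausible. The hematologic table carries the same Day 1 header, yet its lead-in covers "toxicity demonstrated during a mid-cycle visit and/or at the time of laboratory assessment".

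Neither reading requires recovery before re-dosing.

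**3. Is there a rule elsewhere?** Section 6.2.1 (delay for toxicity) and section 5.4 (stopping for unacceptable adverse events) state no grade. Section 6.2.1.3 separates resolving from persisting toxicity, but only for neurotoxicity. Section 6.3 holds capecitabine for any grade 3 or 4 toxicity until grade 1 or less, but it governs chemoradiation, not FOLFIRINOX. No rule fills the gap.

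**4. How many patients?** The inputs are 12.7% grade 3/4 diarrhea (section 6.1.1.2), 50 patients (section 14.2), up to 8 cycles (section 5.2), and six months of planned therapy in the trial that supplied the rate (section 2.2.4), which is 12 to 13 two-week cycles.

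- Unscaled: 0.127 × 50 = 6.35.
- Scaled to 8 cycles, assuming risk proportional to cycles: 0.127 × 8/12 × 50 = 4.2, and 0.127 × 8/13 × 50 = 3.9.

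These are all grade 3/4 cases. The documents do not say what share is still at grade 3-4 on the next Day 1. With an assumed share of 5% to 20%:

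- Low end: 3.9 × 0.05 = 0.2 patients.
- High end: 6.35 × 0.20 = 1.3 patients.

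**5. Is a low share plausible?** Section 2.1.3 puts delayed diarrhea at 2 to 4 days after the dose, lasting 5 to 7 days. It therefore ends between day 2 + 5 = 7 and day 4 + 7 = 11. Re-dosing at 14 days with the +3/-1 window of section 6.2.1 falls on day 13 to 17. The gap is 13 - 11 = 2 days at the shortest and 17 - 7 = 10 days at the longest. This is indicative only, because that section describes weekly irinotecan.

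Section 6.1.1.2 gives no mucositis rate, so that part cannot be sized.

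**The case against.** The strongest reply is that delay for active toxicity is plainly foreseen. Section 6.2.1 allows it, section 5.2 requires treatment to follow the institutional standard of care, section 5.4 provides for stopping, and section 4.1 sends issues that would delay treatment to the principal investigator. Nothing compels dosing into grade 3-4 toxicity, and physician discretion is not the only safeguard. All of that stands. But none of these clauses sets a recovery level, and the same clauses cover neutropenia and nausea/vomiting, for which explicit holds were still written.

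Second, the comparison is thinner than three against two suggests. Two comparators are blood counts, so within the non-hematologic table it is one row against two. Those two rows also remove the bolus permanently, which may be a deliberate, different response. That is fair, but dropping the bolus does not settle when to re-dose.

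Third, the scope can look arbitrary. Grade 3/4 fatigue (23.2%) and ALT elevation (7.3%) have no row at all and rest on the same general clauses. This stands as a limit: the point concerns only rows that state an action and leave out the hold.

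Fourth, the 5% to 20% share has no source in the documents, and the timing in section 2.1.3 suggests that the usual case has resolved before re-dosing. The number affected may be zero.

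Last, grade 2 is a choice; section 6.3 uses grade 1 for capecitabine. Grade 2 fits this table better, because the nausea/vomiting row uses it and the grade 2 diarrhea and mucositis rows already allow treatment at a reduced level.

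**Conclusion.** The point holds, at low severity. Two of the five grade 3-4 rows give a dose action without a hold or a recovery level, and nothing else in the protocol supplies one for diarrhea or mucositis during FOLFIRINOX. The omission is certain from the text; harm from it is not. For diarrhea the expected number affected is 0.2 to 1.3 of 50, and possibly none. That range rests on the cited 12.7% rate, proportional scaling at its lower end, and an assumed 5% to 20% share still at grade 3-4 on Day 1. Mucositis is not quantified. No effect on the R0 resection endpoint is claimed.

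**What to change.** Add one sentence to each of the two rows: if grade 3-4 is present on the planned Day 1, hold all drugs until it falls to grade 2 or less, then resume irinotecan and infusional 5-FU at permanent dose level -1, without the 5-FU bolus and with oxaliplatin unreduced. Leave the grade 2 rows, the header and the rule for which grade sets the dose level as they are, so that no new permanent reductions follow.

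The cost is a short protocol amendment. The study calendar in section 9 already has a toxicity assessment on Day 1 of each cycle, so no new visit or test is needed. The only downside is a short cycle delay for the few patients, if any, who are still at grade 3-4 that day.
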